### **Dose reduction, dose interruption and permanent discontinuations**

The number (%) of subjects with any dose changes (incl. reductions, interruptions, or permanent discontinuations) and the reasons (e.g. AE, dosing error, dispensing error) will be taken from the ‘Study Treatment eCRF’ and summarized by study treatment component. The total duration of interruptions by subject will be summarized for the study population by time intervals, e.g., <1week, ≥1-<2 weeks, ≥2-<3 week etc. (these time intervals may be adjusted depending on the observed data).

### **Cycle initiated and cycle length**

The number of cycles initiated by subject will be summarized. The cycle length (i.e., duration of cycle) by subject will also be summarized by cycle based on summary statistics and categorical analyses (e.g., cycle length <35 days, ≥35-<42 days, ≥42-<56 days, ≥56-<70 days, ≥70 days etc.). Details on derivation are provided in [Appendix Section 5.1](#).

## **2.4.2 Prior, concomitant and post therapies**

Concomitant medications and significant non-drug therapies prior to and after the start of the study treatment will be summarized according to the Anatomical Therapeutic Chemical (ATC) classification system.

Prior anti-neoplastic medications will be summarized using the FAS. Medications will be summarized by ATC class and preferred terms. Prior surgery and radiotherapy treatments will be listed only. Anti-neoplastic medications after discontinuation of study treatment during follow-up within the study will be summarized by ATC class and preferred term. HSCTs will be also summarized with the source, the type of transplant and the allogeneic donor type. Both analyses will be using the FAS.

All transfusions of blood products (incl. those not related to AML) prior and after start of study treatment will be listed and only AML-related transfusions will be summarized using the FAS. For that, the number of transfusion units will be normalized by time (e.g., fixed 8-weekly interval, mentioned below as episode) prior to and on-treatment (overall and by reason due to study indication (no/yes)). The number of subjects with at least one transfusion episode and the number of units per episode will also be described. Further analyses to summarize transfusion independence and dependence are described in the efficacy section.

## **2.5 Analysis of the primary objective**

The primary objectives of the study are to assess the complete remission (CR) rate of MBG453, administered at 800 mg Q4W in combination with azacitidine and venetoclax (CR rate analysis). This is preceded by the safety run-in part in which the primary objective is to determine whether MBG453 at the two tested dose levels is not meeting overdose criteria when added in combination with azacitidine and venetoclax (DLT analysis).

### **2.5.1 Primary endpoint**

#### **DLT analysis (safety run-in part)**

For the DLT analysis, the primary endpoint is the incidence of DLTs between Cycle 1 Day 8 and the end of Cycle 2 of treatment in subjects enrolled in the safety run-in part and included in the DDS.

Details on the definition of DLT which are to be captured in the Adverse Event eCRF were defined in Table 6-4 of the protocol that was copied into [Table 2-2](#) below.

**Table 2-2 Criteria for defining dose-limiting toxicities during the safety run-in**

Toxicity	DLT Criteria
Hematology	Because marrow aplasia is an expected consequence of AML and their therapy, for patients participating in this study, only persistent grade 4 neutropenia, thrombocytopenia and pancytopenia beyond Day 42 from the start of a study treatment cycle and is not related to leukemic infiltration will be considered to be a DLT (bone marrow evaluation may be required to determine if marrow aplasia is due to leukemia).
Vascular disorders	Hypertension CTCAE Grade 3 persisting for > 7 days after treatment is administered.
General disorders and administration site conditions	Infusion reaction CTCAE Grade 3 that does not resolve to Grade 1 within 72 hours or CTCAE Grade 4 of any duration.
Immune	Immune-related adverse events $\geq$ CTCAE Grade 3 persisting > 7 days after treatment with corticosteroids
Ocular	Eye pain or reduction of visual acuity $\geq$ CTCAE Grade 2 that does not respond to topical therapy and does not improve to Grade 1 severity within 2 weeks of the initiation of typical therapy OR requires systemic treatment
Pulmonary	Pneumonitis $\geq$ CTCAE Grade 2 persisting > 7 days despite treatment with corticosteroids
	Pneumonitis $\geq$ CTCAE Grade 3
Skin and subcutaneous tissue disorders	Photosensitivity $\geq$ CTCAE Grade 3 for > 7 days after treatment
	Rash $\geq$ CTCAE Grade 3 for > 7 days after treatment
	Rash CTCAE Grade 4
Gastrointestinal disorders	Diarrhea CTCAE Grade $\geq$ 3 $\geq$ 48 hrs., despite the use of anti-diarrhea therapy
	Nausea/ vomiting CTCAE Grade $\geq$ 3 $\geq$ 48 hrs., despite the use of anti-emetic therapy
	Pancreatitis CTCAE Grade $\geq$ 3
Investigations	Total blood bilirubin increase $\geq$ CTCAE Grade 2 with $\geq$ Grade 2 ALT/AST
Other	Other clinically significant toxicities, including a single event or multiple occurrences of the same event that lead to a dosing delay of > 7 days in cycle 1, or result in an inability to deliver $\geq$ 75% of the planned dose intensity for any of the study drugs in a cycle of treatment because of treatment-related toxicity.

Toxicity	DLT Criteria
	Any other unacceptable toxicity encountered by a subject as determined by the Investigators and Novartis.
Exceptions to DLT Criteria	


Grade 3 fatigue, asthenia, fever, anorexia, or constipation

Grade 3 nausea, vomiting or diarrhea not requiring tube feeding, total parenteral nutrition, or prolonged hospitalization

Infection, bleeding, or other expected direct complication of cytopenias due to active underlying leukemia

Grade 3 or 4 tumor lysis syndrome if it is successfully managed clinically and resolves within 7 days without end-organ damage

Grade 3 or 4 isolated laboratory abnormalities that last ≤3 days

	

### CR analysis (safety run-in and expansion parts)

For the CR analysis, the primary endpoint is the proportion of subjects included in the FAS and assigned to MBG453 at the 800 mg Q4W dose level (in both safety run-in and expansion parts) who achieved a complete remission (CR) as per investigator assessment.

Details on the definition of response categories which are to be captured in the eCRF by the investigator were defined in Table 8-2 of the protocol that was copied into [Table 2-3](#) below.

**Table 2-3 Response classification in AML at a given evaluation time (based on IWG Cheson et al 2003, ELN 2017 Döhner et al 2017)**

Response Category	Definition 
Complete Remission	
Bone marrow:
 

< 5% blasts

no blasts with Auer rods

 
Peripheral blood:
 

neutrophils <math>\geq 1.0 \times 10^9/L</math>

platelets <math>\geq 100 \times 10^9/L</math>

no circulating blasts

 
No evidence of extramedullary disease (such as CNS or soft tissue involvement).

Complete remission with incomplete hematologic recovery (CRi)	
Bone marrow:
 

< 5% blasts

no blasts with Auer rods

 
Peripheral blood:
 

neutrophils <math>< 1.0 \times 10^9/L</math> or platelets <math>< 100 \times 10^9/L</math>

no circulating blasts

Response Category	Definition 
	No evidence of extramedullary disease (such as CNS or soft tissue involvement).
Morphologic leukemia free state (MLFS)	
Bone marrow
 
 
• < 5% blast
 
• no blasts with Auer rods
 
 
No evidence of extramedullary disease (such as CNS or soft tissue involvement)

Partial Remission (PR)	
Bone marrow:
 
 
• < 5% blasts AND presence of blasts with Auer rods
 
 
OR
 
 
• ≥ 50% decrease from baseline in blasts in bone marrow AND blast count in bone marrow is 5% to 25%
 
 
Peripheral blood:
 
 
• neutrophils ≥ 1.0 x 10^9/L
 
• platelets ≥ 100 x 10^9/L
 
• no blasts
 

Progressive Disease (PD)	
Evidence for an increase in bone marrow blast percentage and/or increase of absolute blast counts in the blood
 
 
• >50% increase in marrow blasts from maximum remission or baseline ,whatever is lower (a minimum 15% point increase is required in cases with <30% blasts at baseline; or persistent marrow blast percentage of >70% over at least 3 mo; without at least a 100% improvement in ANC to an absolute level (>0.5 X 10^9/L [500/µL], and/or platelet count to >50 X 10^9/L [50 000/µL] nontransfused); or
 
• >50% increase in peripheral blasts (WBC X % blasts) to >25 X 10^9/L (>25 000/ µL) (in the absence of differentiation syndrome); or
 
• New extramedullary disease
 

Stable disease (SD)	Absence of CR, CRi, PR, MLFS, and criteria for PD or relapse are not met
Relapse from CR or CRi	
Only in patients with a CR or CRi . Any of the following:
 
 
• Reappearance of blasts in peripheral blood
 
 
OR
 
 
• ≥ 5% blasts in bone marrow
 
 
OR
 
 
• (Re-)appearance of extramedullary disease
 

Unknown	In case the response assessment was not done or the assessment was incomplete

The investigator does not determine best overall response, he/she is assessing only the response based on the given bone marrow and peripheral blood data, as well as on the presence or absence of extramedullary disease. The best overall response is the best disease response recorded from the start of the treatment until the first occurrence of relapse or death. Best response will be derived by Novartis for each subject as one of the following: CR, CRI, MLFS, PR, SD, PD, and unknown for all other cases.

The primary estimand related to CR rate is described by the following attributes:

1. Population: subjects with newly-diagnosed acute myeloid leukemia (AML) who are not suitable for intensive induction chemotherapy as defined by inclusion/exclusion criteria and who are assigned to the MBG453 800 mg Q4W dose level.
2. Primary variable: percentage of subjects achieving a complete remission (CR) as per investigator assessment.
3. Treatment of interest: the investigational treatment MBG453 at the 800 mg Q4W dose level combined with azacitidine and venetoclax; the treatment of interest can be also a monotherapy or a combination of two of the three drugs because subjects unable to tolerate one or two of the study treatment drugs may continue study treatment with only the tolerated drug(s) as long as the subject benefits as per investigator's judgement.

Handling of intercurrent events:

- Failure to receive any component of the assigned treatment strategy due to any reason will be handled using treatment policy strategy because the nature of the treatment strategies includes the possibility that MBG453 or azacitidine or venetoclax is discontinued while the other treatment component is continued as long as the subject benefits. Thus, all CR will be taken into account regardless of any study treatment interruption or permanent discontinuation.
- Start of new anti-neoplastic therapy before observing a CR will be handled using the hypothetical strategy because the new anti-neoplastic therapy has the potential to confound the interpretation of effect of the treatment strategy. Thus, a subject with a first CR after the time he/she receives any further neoplastic therapy will not be considered with a CR.
- Hematopoietic stem cell transplantation (HSCT) is a rare opportunity for subjects in remission and thus, an outcome of the treatment. Therefore, the effect of interest integrates the outcome HSCT. A subject with a first CR after the time he/she receives HSCT will not be considered with a CR.

## **2.5.2 Statistical hypothesis, model, and method of analysis**

### **DLT analysis (safety run-in part)**

A Bayesian model will be used to assess whether MBG453 at the two tested dose levels is not meeting overdose criteria when added to azacitidine and venetoclax in subjects from the DDS. The relationship between dose and the probability of DLT is modeled using a logistic regression detailed in Appendix Section 16.1 of the protocol.

A summary of the characteristics of this Bayesian model is presented below:

- A single logistic model will assess the toxicity risk of this triple combination rather than quantifying the contribution of each of the three compounds and their interactions.
- Prior information consists of historical data for 90% and a robustification component for 10%.
- The prior risk of excessive toxicity (i.e. risk of DLT within [33%-100%]) is 4.9% for the MBG453 400 mg Q4W and 5.4% for the MBG453 800 mg Q4W.
- Decisions to start the second cohort and the expansion part are guided by the escalation with overdose control (EWOC) principle (Babb et al 1998): it will be recommended to newly enrolled subjects (in the second cohort or in the expansion part) if the risk of excessive toxicity is less than 25%.

After each cohort in the safety run-in part, the posterior distribution for the risk of DLT for new subjects at the dose level of interest will be evaluated. The posterior distributions will be summarized to provide the posterior probability that the risk of DLT for each dose level of MBG453 lies within the interval [33%, 100%] (i.e. excessive toxicity).

#### **CR analysis (safety run-in and expansion parts)**

A Bayesian design will be used to estimate the CR rate in subjects from the FAS assigned to the MBG453 800 mg Q4W dose level and to provide inferential summaries (e.g., mean, median, standard deviation, 95% credible intervals, and interval probabilities) based on Bayesian posterior distribution of the CR rate. Assuming a uniform informative prior distribution (Beta(1,1)), the distribution of the CR rate will be updated with all available data from the subjects included in the FAS and assigned to the MBG453 800 mg Q4W dose level. This dual-criterion design will allow to base trial success not only on the statistical significance for superiority against the control (CR exceeds the null-value) but also by considering a minimum clinically estimated effect size (CR exceeds the decision value).

The decision criteria for trial success are the following:

1. Statistical significance: the posterior probability that CR rate is  $> 50\%$  (null value) is at least 97.5%
2. Clinical relevance: the posterior median of CR rate is  $\geq 61\%$  (decision value).

The posterior distribution will be used to derive the probability that the true CR rate is superior to 50%. The results will be also presented with a frequentist formulation. The CR rate and the exact 95% confidence interval (CI) ([Clopper and Pearson 1934](#)), as well as the 1-sided p-value via exact Fisher test will be provided in subjects from the FAS assigned to the MBG453 800 mg Q4W dose level. The test will be performed using an overall one-sided 2.5% level of significance. Thus, the null hypothesis ( $H_0: CR \leq 50\%$ ) will be rejected if the lower bound of the two-sided 95% exact CI is  $> 50\%$ .

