Immunogenicity: Data analysis	
Immunogenicity samples will be obtained and evaluated in all subjects.
 
For subjects included in the safety run-in part, the tolerability of MBG453 administered in combination with venetoclax and azacitidine will be guided by a Bayesian analysis and the DLT incidence reported during the two first cycles. The probability that the true DLT rate exceeds 33% will be modeled using a Bayesian Model.
 
For all subjects (safety run-in and expansion parts) treated with MBG453 at 800 mg Q4W, the efficacy of MBG453 in combination with venetoclax and azacitidine will be based on the proportion of subjects achieving a complete remission (CR) as per investigator assessment. Trial success will be assessed based on dual decision criterion with a null value (no effect) of 50% (statistical criteria) and a minimum estimated effect size (clinical relevance) of 61% (clinical criteria) for the CR rate. If the statistical and clinical criteria are both met, the trial will be declared successful.

1 Introduction

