12.4.4 Sensitivity and Supportive analyses

Sensitivity analyses (if appropriate) will be described in the Statistical Analysis Plan.

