#### **2.5.4 Sensitivity and Supportive analyses**

##### **CR analysis (safety run-in and expansion parts)**

The complete response (CR) rate with the exact 95% confidence interval will be presented for subjects assigned to the MBG453 400 mg Q4W dose level, as well as for all subjects from the FAS.

A listing of all derived efficacy endpoints by subject will also be provided including BOR, OS time, OS end date and duration of response. In addition, for some selected laboratory parameters and for bone marrow blasts percentage, trends over time (baseline and on-treatment timepoints during the first 12 cycles of treatment) will be displayed via boxplots and corresponding tables displaying the summary statistics for these selected timepoints be produced.

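### SAP 2.5.2 takes the one-sided p-value for the CR rate from a Fisher exact test, which cannot test a single arm against a fixed 50%; an exact binomial test is needed (minor)

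*SAP*

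**What the plan says.** SAP 2.5.2 (CR analysis) introduces its success rule with "The decision criteria for trial success are the following" and lists two Bayesian conditions under a Beta(1,1) prior: a posterior probability of at least 97.5% that the CR rate exceeds 50%, and a posterior median of at least 61%. The protocol summary agrees: "If the statistical and clinical criteria are both met, the trial will be declared successful".

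The SAP then adds: "The results will be also presented with a frequentist formulation". This part consists of the CR rate, a Clopper-Pearson 95% interval and a p-value: "as well as the 1-sided p-value via exact Fisher test will be provided". It sets a level, "The test will be performed using an overall one-sided 2.5% level of significance", and a rejection rule under which the null of a CR rate of at most 50% "will be rejected if the lower bound of the two-sided 95% exact CI is" above 50%.

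Protocol 12.4.2 contains the same frequentist paragraph but names no test for the p-value. SAP 1.1 describes a single-arm study without randomization, and SAP 1 reports 85 patients treated at 800 mg.

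**The concern.** Fisher's exact test works on a contingency table with at least two groups. Here there is one group, and the 50% reference is a constant with no counts behind it. A programmer following the SAP literally has no second row for the table. The only ways forward are to depart from the text or to invent a comparator, and in the second case the p-value would depend on the invention.

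What is at stake is the correctness of one printed number on the primary endpoint, and its agreement with the interval printed beside it.

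A smaller point concerns the same paragraph. The frequentist part carries a level and a rejection rule but is not called supportive. It is also not listed under SAP 2.5.4, which gives the exact interval only for the 400 mg group and for all subjects. At one responder count, the criterion headed statistical significance is met while the null is not rejected, and nothing says how to word that.

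**Working it through.** **Inputs.** Null 50%, Beta(1,1) prior, thresholds 97.5% and 61%, one-sided level 2.5%, Clopper-Pearson rule (SAP 2.5.2). Planned n = 80, cutoff 49 (SAP 3). Treated at 800 mg: 85 (SAP 1). All 85 belong to the FAS, because the FAS requires only one dose of any component (SAP 2.2).

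**Formulas, for r responders among n.**
- Posterior: Beta(1 + r, 1 + n − r).
- One-sided exact binomial p: P(X ≥ r) for X ~ Bin(n, 0.5).
- Clopper-Pearson lower bound: the 2.5% quantile of Beta(r, n − r + 1).

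The lower bound exceeds 50% exactly when the binomial p is below 0.025. The exact binomial test is therefore the test that the stated rejection rule implies.

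**The plan's own figures, n = 80.** At 49/80 the posterior median is 61.07% and the posterior probability is 0.9776 (printed as 61.1% and 0.978). P(X ≥ 49) is 0.0283 at a true rate of 50% and 0.7951 at 65% (printed as 2.8% and 79.5%). All reproduce.

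**Bayesian rule and exact test at the boundary.**

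| Result | Posterior median | P(CR > 50%) | Bayesian success | Exact p | Lower bound | Null rejected |
|---|---|---|---|---|---|---|
| 48/80 | 59.84% | 0.9626 | no | 0.0465 | 48.44% | no |
| 49/80 | 61.07% | 0.9776 | yes | 0.0283 | 49.70% | no |
| 50/80 | 62.29% | 0.9872 | yes | 0.0165 | 50.97% | yes |
| 51/85 | 59.85% | 0.9669 | no | 0.0410 | 48.80% | no |
| 52/85 | 61.004% | 0.9801 | yes | 0.02513 | 49.988% | no |
| 53/85 | 62.16% | 0.9885 | yes | 0.0147 | 51.18% | yes |

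**Why they differ by one responder.** With a uniform prior and a null of 50%, one minus the posterior probability is the average of P(X ≥ r) and P(X ≥ r + 1), which is the mid-p value. At 52/85: (0.025125 + 0.014728)/2 = 0.0199, and 1 − 0.0199 = 0.9801. The exact test uses the larger tail alone, 0.025125, and just misses 0.025.

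**How often the single count would occur, n = 85.** P(exactly 52) = P(X ≥ 52) − P(X ≥ 53):
- true rate 50%: 0.0251 − 0.0147 = 1.0%
- true rate 60%: 0.4589 − 0.3725 = 8.6%
- true rate 65%: 0.8039 − 0.7363 = 6.8%

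**The case against.** The best defence is that little depends on the label. The success criteria are listed explicitly and are both Bayesian, the frequentist results are presented in addition, and the rejection rule uses the exact interval. The interval also makes the intended test plain. All of this stands, and it is why the point is minor. It does not rescue the wording: the named test cannot be run on these data, whatever the result.

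A reader might go further and infer that the plan has two competing success rules. The documents do not support that. The protocol summary, SAP 2.5.2 and the sample-size sections all define success by the two Bayesian criteria. Nor is the error rate hidden: both documents print 2.8% for the 49/80 rule, which is also the exact p-value at 49/80.

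A reader might also cite protocol 12.7, which places formal testing at full alpha at the primary analysis, as raising the exact test to a confirmatory role. That sentence does not say which test it means. It sits in the interim-analysis section and reads naturally as saying that alpha is not split across analyses.

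Protocol 12.4.4 says: "Sensitivity analyses (if appropriate) will be described in the Statistical Analysis Plan". That the 800 mg test is absent from SAP 2.5.4 is therefore a gap in labelling, not evidence that it governs.

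Finally, the disagreement at n = 85 is very thin. At usual rounding, 52/85 would print as p = 0.025 with a lower bound of 50.0%. The n = 80 case now matters only as a property of the planned design.

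**Conclusion.** The point holds as a wrong method label of minor severity. The p-value in SAP 2.5.2 should come from a one-sided exact binomial test against 50%. Success under the Bayesian criteria and rejection through the Clopper-Pearson bound are unaffected. The plan's own cutoff, type I error and power reproduce, so there is no arithmetic error.

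As a side note, the Bayesian rule and the exact test disagree at one responder count for each sample size: 49 of 80 as planned, and 52 of 85 as treated, where the exact test needs 53. This rests on all 85 subjects treated at 800 mg being in the FAS, and on the exact bound being used as written; a mid-p version would reject at both counts (0.0224 and 0.0199). The missing supportive label would matter only if the result fell on exactly 52.

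**What to change.** In SAP 2.5.2, replace the reference to the exact Fisher test with: *one-sided exact binomial test against 50%*. Keep the interval, the level and the rejection rule as they are.

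Optionally, add one sentence to the same paragraph: *The frequentist results are supportive; the Bayesian dual criterion alone determines trial success.* That would prevent a contradictory statement in the report at 52/85.

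The cost is a few words before database lock. There is no protocol amendment, because protocol 12.4.2 names no test, and no new data, no change to the success rule and no analysis removed. An entry in SAP 4 is not required.
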